9.7.1.2. Descriptive statistics

The distributions of baseline characteristics at time zero by exposure group will be calculated to describe the study cohort and illustrate differences between the groups. Means, standard deviations, medians, and other quartiles will be estimated for continuous variables. Counts and proportions will be estimated for categorical variables. The missingness of variables will also be described. The interim report will be limited to descriptive analyses. Comparative analyses will be included in the final report. Further details will be described in the SAP.

To describe the relative imbalance of characteristics between exposed and unexposed groups, absolute standardised differences will be calculated for each baseline characteristic.^{37,38} An overall standardised difference across all levels will be calculated for multilevel categorical variables.³⁸ The balance will also be checked after propensity score methods are applied to control for any confounding. Further details will be described in the SAP.

9.7.1.3. Description of vaccination trajectories

Each exposure group of the matched cohort will be characterized in the following categories:

- Counts and percentages of individuals receiving a subsequent COVID-19 vaccine;
- Brand of subsequent COVID-19 vaccine;
- Time to administration of subsequent vaccine.

9.7.1.4. Crude outcome measures

For safety outcomes with a known short risk interval ([Table 1](#)) (e.g., anaphylaxis), the risk (number of events/number of individuals in a cohort) and the corresponding 95% CIs will be computed. Effect estimates will be calculated both as risk differences and as risk ratios, with their corresponding 95% CIs, for those exposed to a Pfizer-BioNTech COVID-19 bivalent vaccine compared with the unexposed group that did not receive any COVID-19 vaccine during follow-up.

For safety outcomes with unknown risk intervals or those that require long follow-up (eg, death), the cumulative incidence will be computed, which will be estimated using the 1 – Kaplan-Meier estimator. Time to outcome will be defined as the time from the baseline date (time zero) until the occurrence of the outcome or censoring (Section 9.1.1.4 and Section 9.7.1.7). The variance will be computed using approaches that account for autocorrelation (eg, the robust estimator or via bootstrapping).^{39,40} Risk differences and risk ratios (and their corresponding 95% CIs) will be estimated at different time intervals, which will be adapted to the specific nature of each outcome.

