9.1.1.4. Follow-up

Individuals will be followed from time zero until the end of the study period (31 August 2024, or 30 June 2025 for pregnancy outcomes), the occurrence of the AESI being analysed, death, or disenrollment from the data source, whichever occurs first. Additionally, the

PFIZER CONFIDENTIAL

CT24-WI-GL02-RF02 4.0 Non-Interventional Study Protocol Template For Secondary Data Collection Study

01-Jun-2022

Page 18 of 64

matched pair will be censored when the unexposed individual of the pair receives any COVID-19 vaccine or when the exposed individual in the pair receives a non-Pfizer vaccine.

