Respiratory system	Acute respiratory distress syndrome	365	Cohort
Reproductive system	Secondary amenorrhea	183	Cohort
	Hypermenorrhea	183	Cohort
Skin and mucous membrane, bone and joints	Erythema multiforme	42	Cohort
	Chilblain-like lesions	42	Cohort
Other	Anosmia, ageusia	42	Cohort
	Anaphylaxis ^a	1 ³¹	Cohort/SCRI
	Multisystem inflammatory syndrome	42	Cohort
	Death (any causes)	365	Cohort
	Subacute thyroiditis	365	Cohort
	Sudden death	365	Cohort
Pregnancy outcome, maternal	Gestational diabetes	Any time pregnancy	Sub-cohort
	Preeclampsia	After 20 weeks gestation	Sub-cohort
	Maternal death	Any time pregnancy	Sub-cohort
Pregnancy outcome, neonates. Define design taking trimester into account	Foetal growth restriction	Any time pregnancy	Sub-cohort
	Spontaneous abortions	At spontaneous abortion	Sub-cohort
	Stillbirth	At birth	Sub-cohort
	Preterm birth	At preterm birth	Sub-cohort
	Major congenital anomalies ^a	1 year after birth	Sub-cohort
	Microcephaly	At birth	Sub-cohort
	Neonatal death	At birth	Sub-cohort
Termination of pregnancy for foetal anomaly	At termination	Sub-cohort	

090177e19fa902a7Approved\Approved On: 12-Jan-2024 21:20 (GMT)

Table 1. Safety outcomes: adverse events of special interest (AESIs) with estimated risk intervals and preferred study design

Body system / classification	Adverse event of special interest	Estimated risk interval (days)*	Preferred study design*
	Small size for gestational age	Any time pregnancy	Sub-cohort
Any	Severe COVID-19 ^b	Any	Cohort

SCRI = self-controlled risk interval

* Time zero corresponds to the day of vaccination (i.e., a 42-day risk interval means that individuals are followed from the day of vaccination to day 41). Risk interval based on the ACCESS project results and other publications.

a For these AESI clinical validation will occur.

b Severe COVID-19 defined as either COVID-19 hospitalisation or death

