9.7.1. Cohort design

9.7.1.1. Exposure assignment and follow-up

The main exposure of interest is in the receipt of at least one dose of the bivalent BA.1 or bivalent BA.4-5 vaccine. Individuals will be assigned to each vaccination category according to their data at time zero, as outlined below:

- **Exposed cohort:** Individuals will be assigned to this cohort when they receive a first dose of the bivalent BA.1 or bivalent BA.4-5 vaccine. Individuals will be censored if they receive a non-Pfizer COVID-19 vaccine during follow-up. For the matched comparative analyses individuals will be censored when their matched pair is censored.
- **Unexposed cohort:** Individuals will be assigned to this cohort if they have not received a COVID-19 vaccine at time zero. Individuals will be censored if and when

PFIZER CONFIDENTIAL

they receive a dose of any COVID-19 vaccine during follow-up. Time zero in the unexposed cohort will be the same day when they did not receive a Pfizer-BioNTech COVID-19 vaccine dose. This day will be chosen by calendar matching to the time zero of the corresponding exposed group.

Individuals will be followed from time zero (see [Section 9.1.1.4](#)) until the censoring described above, death, administrative end of follow-up, or end of study period 31 August 2024, whichever occurs first, with pregnancies followed until 30 June 2025 (see [Section 9.7.1.7](#)). For analyses of AESIs with known risk intervals, follow-up will be truncated at the end of the risk interval.

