9.7.1.8. Censoring

Censoring to analyse individuals with complete follow-up and complete adherence to the vaccination strategies will be done to estimate the total effect of bivalent BA.1 or BA.4-5 vaccination on the risk for the AESIs.

The following censoring will be applied to estimate the total effect under complete follow-up and complete adherence to the vaccination strategies, as well as the corresponding assumptions for validity:

- **Censoring after loss to follow-up** (i.e., disenrollment from the data source). This censoring will be implemented to estimate the effect under complete follow-up. The assumption behind this is that individuals who do not disenroll from the data source have a similar risk of the AESI as the individuals who do disenroll from the data source if they had remained in follow-up, conditional on the matched covariates and other variables that were adjusted for.
- **Censoring due to unexposed individual receiving COVID-19 vaccination.** Censoring of the matched pair when the individual in the unexposed cohort receives a COVID-19 vaccine or when the individual in the exposed cohort receives a non-Pfizer vaccine will occur. This censoring will be implemented to estimate the effect under complete adherence to the vaccination strategies. The assumption behind this is that the risk of the AESI for individuals that did not deviate from the vaccination strategy would be similar to that of the individuals who deviated from the vaccination strategy, had they not deviated, conditional on adjustment of the matched variables and other variables.

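### Short-interval AESI risks are events divided by everyone matched, although the plan censors pairs inside the interval; risks and risk differences therefore shrink toward zero

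*Protocol*

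**What the plan says.** Section 9.7.1.4 sets two estimators. For outcomes with a known short risk interval, "the risk (number of events/number of individuals in a cohort) and the corresponding 95% CIs will be computed", and the risk differences and risk ratios are built on that proportion. The alternative is reserved for the rest: "For safety outcomes with unknown risk intervals or those that require long follow-up (eg, death), the cumulative incidence will be computed", by 1 minus Kaplan-Meier, with time running to the outcome or to censoring. Only in that second paragraph does the section add "The variance will be computed using approaches that account for autocorrelation".

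The censoring rules make no such distinction. Section 9.1.1.4 states that the "matched pair will be censored when the unexposed individual of the pair receives any COVID-19 vaccine"; the same happens when the exposed member receives a non-Pfizer vaccine. Section 9.7.1.1 carries censoring to both members: "For the matched comparative analyses individuals will be censored when their matched pair is censored". For known intervals it adds only that "For analyses of AESIs with known risk intervals, follow-up will be truncated at the end of the risk interval". The footnote to Table 1 in section 9.3.2 fixes the length: "a 42-day risk interval means that individuals are followed from the day of vaccination to day 41". Section 9.7.1.8 gives the purpose of the censoring, which is "to estimate the total effect under complete follow-up and complete adherence to the vaccination strategies".

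**The concern.** A simple proportion estimates the risk over an interval only if everyone in the denominator is observed to the end of it or has the event. Here follow-up can end early by rule, and nothing exempts the short intervals. Followed as written, the plan drops events after censoring from the numerator and keeps the pair in the denominator. The result is not the risk under complete follow-up and adherence that section 9.7.1.8 promises.

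Table 1 gives intervals of 7 to 42 days to most of the AESIs marked for clinical validation: Guillain-Barré syndrome, narcolepsy, thrombocytopenia and transverse myelitis (42 days), thrombosis with thrombocytopenia (15), and myocarditis and pericarditis (7, 14 and 21). Risk differences are a promised effect measure, and in a safety study shrinkage toward zero is the unfavourable direction. The shrinkage also depends on how fast controls are vaccinated. It could therefore differ between data sources and add heterogeneity to the pooling in section 9.7.1.9, chiefly for risk differences.

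**Working it through.** **The plan's own figures.** Table 3 (section 9.5) uses simple proportions and says that it assumes complete follow-up. For 100,000 per group, risk 1 per 5000 and risk ratio 2, the expected events are 40 and 20. SE(log RR) = √(1/40 − 1/100,000 + 1/20 − 1/100,000) = 0.274, and 2 × exp(±1.96 × 0.274) gives 1.17 to 3.42, as printed. All 27 rows reproduce. The table is sound under its assumption; the question is what happens when that assumption fails.

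**Inputs.** Interval lengths W come from Table 1. The share of pairs censored is not in the documents, so c = 20% to 50% by day 42, at a constant rate, is an assumption.

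**Formulas.** The probability that a pair is still uncensored on day t is G(t) = exp(−λt), with λ = −ln(1 − c)/42. That gives λ = 0.00531 for c = 20% and 0.01650 for c = 50%. With a constant hazard and rare events, events/N recovers the fraction (1/W) Σ G(t) of the true risk, summed over t = 0 to W − 1.

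| Interval (days) | Understated, c = 20% | Understated, c = 50% |
|---|---|---|
| 1 | 0% | 0% |
| 7 | 1.6% | 4.8% |
| 14 | 3.4% | 10.0% |
| 15 | 3.6% | 10.7% |
| 21 | 5.1% | 14.8% |
| 28 | 6.8% | 19.3% |
| 42 | 10.1% | 27.3% |

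Placing events at mid-day instead of the start of the day adds at most 0.8 percentage points (42 days: 10.4% to 27.9%).

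**Constant effect.** Both members of a pair share G(t), so it cancels from the ratio. The risk ratio is unchanged, and the risk difference shrinks by the percentage in the table. For example, with true 42-day risks of 40 and 20 per 100,000 and c = 50%, the recovered fraction is 30.55/42 = 0.727. The estimates become 29.1 and 14.5, a risk difference of about 14.5 instead of 20, and the ratio stays 2.00.

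**Effect that varies within 42 days.** Let m(t) be the daily rate ratio. The estimated ratio is Σ m(t)G(t) / Σ G(t). The sums of G are:

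- c = 20%: 37.74 over all 42 days, 6.89 over days 0–6, 24.22 over days 14–41.
- c = 50%: 30.55, 6.665 and 17.94 respectively.

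A 3-fold effect on days 14–41:
- True ratio 1 + 2 × 28/42 = 2.33.
- Estimated 1 + 2 × 24.22/37.74 = 2.28 (c = 20%), or 1 + 2 × 17.94/30.55 = 2.17 (c = 50%).
- Risk difference low by 1 − 24.22/28 = 14%, or 1 − 17.94/28 = 36%.

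A 5-fold effect on days 0–6:
- True ratio 1 + 4 × 7/42 = 1.67.
- Estimated 1 + 4 × 6.89/37.74 = 1.73, or 1 + 4 × 6.665/30.55 = 1.87.
- Risk difference low by 1 − 6.89/7 = 1.6%, or 1 − 6.665/7 = 4.8%.

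**Cross-check by simulation.** Two million pairs were simulated over 42 days, with true risks of 400 and 200 per 100,000, the excess in the first 7 days, and censoring spread evenly. At c = 10%, 30% and 50%, events/N gave ratios of 2.07, 2.16 and 2.29. One minus Kaplan-Meier gave 2.02 to 2.03 each time.

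**The case against.** The strongest counter-argument is that the primary question is whether risk is increased, and pair-censoring cannot create a signal. With no effect, the expected ratio stays 1 and the difference 0, whatever the censoring. That stands. The ratio shifts are also small beside the plan's own precision: at 100,000 per group, risk 1 per 50,000 and ratio 2, Table 3 gives 0.37 to 10.92. Anaphylaxis, the section's own example, has a 1-day interval and is essentially untouched.

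The heading says crude, and adjusted estimates follow in section 9.7.1.6. This does not answer the point: those weights are described for baseline confounding, not censoring, and the long-interval crude measure in the same section does handle censoring. The self-controlled analysis has no matched controls to censor and covers most short-interval AESIs. It is secondary, however, it gives rate ratios and not risk differences, and Table 1 lists erythema multiforme, chilblain-like lesions, anosmia/ageusia and multisystem inflammatory syndrome (all 42 days) for the cohort design only.

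A reader might infer two stronger claims, and the documents support neither:

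- That many controls will certainly be vaccinated within the interval. Matching on age band, residence and vaccination history among people targeted for the vaccine makes this plausible, but no uptake speed is given. Section 9.7.1.3 plans to describe time to the next vaccine, so the extent will become visible.
- That confidence intervals for these AESIs wrongly treat reused controls as independent. Section 9.7.1.4 does not state the short-interval variance method, which can be left to the SAP. Section 9.1.1.3 limits reuse to different time periods, which restricts overlap even if it does not clearly exclude it.

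**Conclusion.** The inconsistency is in the protocol text: a denominator that presumes complete observation is paired with a rule that ends observation early, and no section reconciles them. The direction for risks and risk differences is certain, toward zero, wherever censoring occurs inside the interval. The size rests on the assumed 20 to 50% censored by day 42 at a constant rate. Under it, risks are understated by about 0% at 1 day, 2–5% at 7, 3–10% at 14, 5–15% at 21, 7–19% at 28 and 10–28% at 42 days. With less censoring the loss falls roughly in proportion. The null and any constant risk ratio are preserved; ratios move only when the effect varies within the interval, in either direction. This should be fixed, but it does not threaten the study's ability to test for no effect.

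**What to change.** In section 9.7.1.4, estimate the risk for every cohort AESI with an interval longer than 1 day by the 1 minus Kaplan-Meier cumulative incidence already specified for long-interval outcomes, evaluated at the end of the Table 1 risk interval. Derive the risk differences and ratios from it. Keep the simple proportion only for the 1-day anaphylaxis interval. For consistency, extend the robust or bootstrap variance named in the second paragraph to these estimates; this is an accompanying improvement, not the correction of a demonstrated error. The cost is a short change to the protocol and SAP text and minor extra programming, with no additional data.

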9.3.2. Outcomes

The list of AESIs to be analysed as outcomes and the preferred study design are based on those proposed by the EMA -sponsored ACCESS project (vACCine COVID-19 monitoring readinESS) and also, for consistency, those included in the ongoing PASS of the Pfizer BioNTech COVID-19 monovalent vaccine (EUPAS41623). The AESIs are listed in Table 1 by body system, with the corresponding risk interval and preferred study design (Section 9.1). Clinical validation will be considered for specific AESIs.

Table 1. Safety outcomes: adverse events of special interest (AESIs) with estimated risk intervals and preferred study design

Body system / classification	Adverse event of special interest	Estimated risk interval (days)*	Preferred study design*
Autoimmune diseases	Guillain-Barré syndrome ^a	42	Cohort/SCRI
	Acute disseminated encephalomyelitis	42	Cohort/SCRI
	Narcolepsy ^a	42	Cohort/SCRI
	Acute aseptic arthritis	42	Cohort/SCRI
	Diabetes mellitus type 1	365	Cohort
	(Idiopathic) thrombocytopenia ^a	42 ^a	Cohort/SCRI
	Thrombosis thrombocytopenia syndrome (TTS) ^a	15 ^a	Cohort/SCRI
	Myositis	365	Cohort
Cardiovascular system	Acute cardiovascular injury including microangiopathy	365	Cohort
	Arrhythmia	365	Cohort
	Heart failure	365	Cohort
	Stress cardiomyopathy	365	Cohort
	Coronary artery disease	365	Cohort
	Myocarditis or pericarditis ^a	7; 14; 21	Cohort/SCRI
	Myocarditis ^a	7; 14; 21	Cohort/SCRI
	Pericarditis ^a	7; 14; 21	Cohort/SCRI
Circulatory system	Coagulation disorders: thromboembolism, haemorrhage	28	Cohort/SCRI

PFIZER CONFIDENTIAL

CT24-WI-GL02-RF02 4.0 Non-Interventional Study Protocol Template For Secondary Data Collection Study

01-Jun-2022

Page 23 of 64

090177e19fa902a7Approved\Approved On: 12-Jan-2024 21:20 (GMT)

Table 1. Safety outcomes: adverse events of special interest (AESIs) with estimated risk intervals and preferred study design

Body system / classification	Adverse event of special interest	Estimated risk interval (days)*	Preferred study design*
	Single organ cutaneous vasculitis	28	Cohort/SCRI
	Cerebral venous sinus thrombosis	28 ²⁸	Cohort/SCRI
Hepato-gastrointestinal and renal system	Acute liver injury	365	Cohort
	Acute kidney injury	365	Cohort
	Acute pancreatitis	365	Cohort
	Rhabdomyolysis	365	Cohort
	Glomerulonephritis	365	Cohort
Nerves and central nervous system	Generalised convulsion	42	Cohort/SCRI
	Meningoencephalitis	42	Cohort/SCRI
	Transverse myelitis ^a	42	Cohort/SCRI
	Bell's palsy	42	Cohort/SCRI

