Individuals would need to be censored at the time of a documented SARS-CoV-2 infection or COVID-19 diagnosis in order to estimate the direct effect only. The likely underreporting of SARS-CoV-2 infections and COVID-19 during the time when bivalent vaccination is available will mean that some of the estimated direct effects could be mediated through the prevention of SARS-CoV-2 infection or COVID-19 by the vaccination. It is expected that this will be important limitations to evaluating the direct effect. Therefore, the main analysis of this study will evaluate the total effect. In addition, sensitivity analyses (Section 9.7.1.11) will be carried out to estimate the direct effect. An additional censoring criterium, i.e., a documented SARS-CoV-2 infection or COVID-19, will be implemented to estimate the direct effect. The assumption behind this is that uncensored individuals will have a similar risk for the AESI as that of the censored individuals if they had not been infected, which is conditional on the matched covariates and other variables that will be adjusted for.

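### For long-interval non-fatal AESIs and sudden death, 1 minus Kaplan-Meier with follow-up ending at death overstates the cumulative incidence it is said to estimate

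*Protocol*

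**What the plan says.** Section 9.7.1.4 of the protocol divides the outcomes in two. Those with a known short risk interval get a simple risk, events over individuals. The rest are introduced with "For safety outcomes with unknown risk intervals or those that require long follow-up (eg, death", death being the only example given, and for these "the cumulative incidence will be computed, which will be estimated using the 1 – Kaplan-Meier estimator". Time runs from time zero "until the occurrence of the outcome or censoring", with no third category. From these curves, "Risk differences and risk ratios (and their corresponding 95% CIs) will be estimated at different time intervals".

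Section 9.1.1.4 ends follow-up at "the occurrence of the AESI being analysed, death, or disenrollment from the data source, whichever occurs first". Section 9.7.1.1 ends it at "until the censoring described above, death, administrative end of follow-up, or end of study period 31 August 2024".

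Table 1 (Section 9.3.2) gives a 365-day interval to 14 non-fatal AESIs, by my count, including "Heart failure", coronary artery disease, arrhythmia and acute kidney injury, and also to death and sudden death. Section 9.7.1.8 lists the censoring events with an assumption for each: loss to follow-up and departure from the vaccination strategy. Death is not among them.

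**The concern.** Kaplan-Meier has two states, event and censored. Once death ends follow-up, a person who dies before a non-fatal AESI is handled like someone who moved away and could still have the event later. One minus Kaplan-Meier then estimates the risk in a population where nobody dies of anything else. That is a different quantity from the cumulative incidence the section says it computes, and it is larger whenever deaths occur. The same applies to sudden death, with which all other deaths compete. For all-cause death nothing competes and the estimator is right.

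The section also mixes two kinds of risk under one name. For short intervals, people who die stay in the denominator as event-free; for long intervals they are removed from the risk set.

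At stake are the absolute risks and risk differences, which are reported effect measures of this safety study. Section 9.7.1.6 applies propensity-score weights to the same risks and cumulative incidences, so the problem is not confined to the crude results.

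**Working it through.** **Scale from the protocol.** The protocol has no figure for this point. Its only computed figures are the precision limits in Table 3, which assume complete follow-up. For 100,000 per group, risk 1 per 5000 and risk ratio 2, the expected events are 40 and 20. SE(log RR) = √(1/40 − 1/100,000 + 1/20 − 1/100,000) = 0.2738, and 2 × exp(±1.96 × 0.2738) gives 1.17 to 3.42, as printed. Table 3 is unaffected and serves here only for scale.

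**Inputs.** One-year mortality is not in the documents; I assume 1% to 20%. AESI risk is 1 per 5000 (Table 3) or an assumed 1% for a common 365-day AESI. Hazards are constant over the year: h = −ln(1 − AESI risk), d = −ln(1 − mortality).

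**Formulas.**
- Death censored: 1 − exp(−h)
- Death competing (the target of Aalen-Johansen): h/(h + d) × [1 − exp(−(h + d))]

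**Absolute risk, 1% AESI** (1 − KM gives 1000 per 100,000 throughout):

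| Mortality | Death competing, per 100,000 | Excess of 1 − KM | Ratio |
|---|---|---|---|
| 1% | 995.0 | 5.0 | 1.0050 |
| 5% | 974.8 | 25.2 | 1.0258 |
| 10% | 949.2 | 50.8 | 1.0535 |
| 20% | 896.5 | 103.5 | 1.1155 |

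The ratio hardly depends on the AESI risk. For 1 per 5000, the excess is 0.1, 1.0 and 2.1 per 100,000 at 1%, 10% and 20% mortality.

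**Contrast, equal mortality.** Hazard ratio 2, 1% AESI risk in the unexposed, 10% mortality in both groups. With death censored: 1990 − 1000 = 990 per 100,000, ratio 1.990. With death competing: 1889.1 − 949.2 = 939.9 per 100,000, ratio 1.990. The ratio is unchanged; the difference is overstated by 990/940 = 1.053, the same factor as the absolute risk.

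**Contrast, unequal mortality.** Hazard ratio 1, 1% AESI risk. With death censored the ratio is 1.000 and the difference 0 in every row.

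| Mortality, exposed v unexposed | Ratio, death competing | Difference per 100,000 |
|---|---|---|
| 0.9% v 1% | 1.0005 | +0.5 |
| 8% v 10% | 1.011 | +10.3 |
| 5% v 10% | 1.027 | +25.6 |
| 10% v 20% | 1.059 | +52.8 |

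**The case against.** Four points on the other side have force.

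A reader might infer that censoring deaths contradicts the declaration "Therefore, the main analysis of this study will evaluate the total effect". The documents do not support that. Section 9.7.1.7 separates total from direct effect only by whether the pathway through SARS-CoV-2 infection is kept; the direct effect comes from additional censoring at documented infection, which the main analysis does not do. All-cause death and severe COVID-19 are also outcomes in their own right. What is left is a tension: censoring deaths removes effects that act through survival, and the protocol does not discuss this.

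A reader might also infer that every risk difference is overstated, or that the estimator always leans towards the vaccine. Neither holds. With a null hazard ratio and lower mortality in the exposed, the death-censored difference is 0 and the competing-risk difference is positive. The ratios of 1.01 to 1.06 cannot be called the true ones either. If the mortality gap is partly healthy-vaccinee selection, the competing-risk contrast carries that confounding into the AESI comparison, whereas the death-censored contrast stays at 1.00.

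The size rests on assumed mortality and is small beside the precision in Table 3. In a general population near 1% mortality it is about 0.5%. Gaps as wide as 10% v 20% are extreme after matching on age, immunocompromise and number of risk conditions. This stands, and it limits the point to the oldest strata and mainly to absolute measures.

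Finally, the text could be called incomplete, not wrong: the only example is all-cause death, and Section 9.7.1.1 names death separately from the censoring before it. But the rule covers all long-interval outcomes and names its estimator outright. The later detail that Section 9.7.1.6 leaves to the SAP concerns variable selection and weights, not this estimator.

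**Conclusion.** The point holds in a limited form. For the 14 non-fatal 365-day AESIs and for sudden death, the named estimator does not deliver the cumulative incidence it is said to estimate, and no assumption is stated for treating death as censoring. Absolute risks are overstated, never understated, by about 0.5%, 5% and 11.5% at assumed one-year mortality of 1%, 10% and 20%. With similar mortality in both groups the risk ratio is essentially unaffected and a raised risk difference is inflated by the same factor as the absolute risk. With unequal mortality the risk ratio can shift by about 1% to 6% for the wider gaps assumed (8% v 10% up to 10% v 20%), and part of that may reflect confounded mortality.

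These sizes assume constant hazards and mortality levels that the documents do not supply. The direction for absolute risk does not depend on the level chosen. The choice of estimator for all-cause death is correct, and the definition of the total effect is not contradicted.

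**What to change.** In Section 9.7.1.4, keep 1 minus Kaplan-Meier for all-cause death. For every other outcome now assigned to it, including sudden death, use the Aalen-Johansen estimator with death from other causes as a competing event, weighted where inverse probability weights are applied. Report the death-censored, cause-specific contrast as supportive and add its assumption to Section 9.7.1.8. Leave the short-interval outcomes as events over individuals.

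Two clarifications fit in the same edit. Section 9.7.1.4 refers to Section 9.7.1.7 for censoring, but that text is in Section 9.7.1.8. Section 9.7.1.1 censors an exposed individual when the matched pair is censored, so it should say whether one member's death does this to the other.

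The cost is a few lines of text and a standard method. Reported absolute risks will be slightly lower. A mortality difference between the groups, confounded or not, can enter the cumulative-incidence contrast, which is why the cause-specific contrast should stand beside it.
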